H₀: The MVN group will have less depression and higher self-efficacy compared to Usual Care.
3. Assess usability and satisfaction with using a smartphone application for participation in a post-CR cardiac health program.
H₀: The MVN group will report high usability and satisfaction with the MVN app.

Study Design

Mixed methods study with a randomized controlled trial and usability study with individual interviews.

Selection of Subjects / Setting

We plan to enroll up to 60 participants from John Muir Medical Center (JMMC). JMMC is a non-profit, community hospital system consisting of two large medical campuses and 3 CR locations (Brentwood, Concord, Walnut Creek). Participants will be randomized through a computer program to either the intervention group (Mvn app) or control group (usual care).

Inclusion criteria:

1. ≥ 18 years of age
2. History of cardiovascular disease that qualified patient for cardiac rehabilitation (i.e., ischemic heart disease, history of unstable angina, systolic heart failure with ejection fraction =/ $< 35\%$ and Class II to IV symptoms, coronary artery bypass graft surgery, valve replacement)
3. Within eight weeks of completing outpatient cardiac rehabilitation

Exclusion criteria:

1. Cognitive impairment
2. Lack of English proficiency/literacy
3. Clinically conditions including:
 - a. Unstable arrhythmias, aortic stenosis, thrombophlebitis, dissecting aneurysm or symptomatic anemia
 - b. Active infection
 - c. Uncontrolled hypertension: resting diastolic > 100 mmHg, systolic > 180 mmHg
 - d. Decompensated heart failure NYHA Class 3-4
 - e. Current unstable angina (No chest pain for a month)
 - f. 2nd or 3rd degree heart block
 - g. Uncontrolled high grade exercise-induced ventricular ectopy-hemodynamically stable

Both Usual Care and MVN Intervention groups

- Upon completion of the CR program, participants will be given their standard instructions and educational handouts
- Individuals will meet with their nurse or other health care provider in an exit interview to review their exercise progress, discuss their future exercise goals and plans, and receive referrals to additional medical services they might need after discharge from the program.
- Baseline clinical measurements, including a 6 minute walk

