- An activity tracker will be given to each participant. Participants randomized to the intervention group will receive a Fitbit and instructions on how to sync their data. Participants randomized to the control group will receive a basic pedometer with a paper diary to record their step counts each day.
- Questionnaires will ask about health care utilization, physical activity, quality of life, and self-efficacy.
- The clinical measurements and psychosocial questionnaires will be taken again at 2-months.
- Participants will be paid \$50 in the form of a gift card for each month they complete. Participants that participate in the individual interview will receive an extra \$25 card. Participants in the intervention group will be allowed to choose whether they would like to keep the Fitbit or receive the gift cards. Participants in the control group will be allowed to keep their pedometer and will also receive the gift cards. If a participant withdraws from the study before month two, they will be asked to return their devices.

MVN Group Only:

- During the final week of outpatient cardiac rehabilitation, the MVN application will be downloaded on to the participant's smartphone or tablet. If the participant does not have a smartphone or tablet, a smartphone will be provided to them for the duration of the study. The participant will be required to return the smartphone at the end of their participation in the study.

- Each participant's individualized instructions for post-cardiac rehabilitation will be integrated into the MVN application including daily medication reminders, physical activity prompts, educational materials, and patient-reported outcome assessment of behavior and psychosocial status.
- Text messages or phone calls will be used on an ad hoc basis to provide positive feedback to the participant. Frequency of messages will depend on adherence level (adaptive intervention).
- We will apply an adaptive intervention: a sequence of decision rules that specify how the intensity or type of treatment should change depending on the patient's needs. We are developing sequential, multiple assignment, randomized trials (SMART) to enable scientists to build adaptive interventions. Interventions that adapt at the right times can improve participant outcomes (e.g., intensifying for people who do not respond to the initial treatment) while decreasing the cost and burden of the intervention (e.g., stepping down treatment for responsive participants).

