- Regular messages will be based on the American Heart Association Simple 7 Principles (3 times a week on random days and between 9am-6pm). Examples include prompting participants to engage in physical activity, track their medicine at certain times of the day, engage in healthy eating habits, or provide participants with a homework assignment to reinforce educational content regarding risk management.
- Any patient reports of chest pain or acute shortness of breath will immediately prompt an automated message on the app to call 911 or their cardiologist/primary care provider. The consent will specify the research members including nurse will only monitor app use but not play an integral role in provided one-on-one coaching.
- A registered nurse or nurse practitioner will be available to triage patient entries once a day (mid-afternoon). Two-way messaging between the participant and the nurse will be available to provide opportunities to answer more specific questions.
- Technical support will be provided by Moving Analytics who has developed and own the MVN app.
- We will assign patients to a group of 6 individuals to offer social support and a "buddy system", which will be a feature in the secure MVN app. Ideas for these groups may be sharing exercise tips/goals/progress, recipes, etc. The groups will be formed with consecutive enrollment. The function of the social group will be iterative with regular feedback from the group members that will be sent to the research assistant to improve this feature.
- Up to six participants from the intervention group will be asked to complete an individual interview to assess the feasibility of and their satisfaction with the mobile app over the two month period.

Study Activities:

Activity	Usual Care	MVN	Intervals
MVN mobile app		X	Intervention period
Educational materials	X	X	Baseline
Activity tracker	X	X	Intervention period
Step count diary	X		Intervention period
Physical activity prompts		X	Intervention period
Nurse feedback (through app or by phone)		X	Intervention period
Psychosocial questionnaires	X	X	Baseline, Month 2

Blood pressure/heart rate	X	X	Baseline, Month 2
Weight	X	X	Baseline, Month 2
6 minute walk	X	X	Baseline, Month 2

Intervention period: 2 months

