**[name], MS, FNP-BC, FAAN, FAHA**

**NCT03446313**

**Statistical Analysis**

**04/23/2019**

P-values for baseline tests were calculated from two-sample t-tests (or Wilcox rank-sum test if skewed) or chi-squared tests.

We analyzed the primary outcome of step count difference between the two groups over 60 days fitting linear mixed-effects models with the step count for each day in R (version 3.6.0). For a more precise estimate of the treatment effect, we used a step-wise procedure to include potential covariates impacting the outcome (age, gender, working status, college or higher education, relationship status, depression, self-efficacy, and self-reported PA), including only terms that were significant in the model. The 2-sided significance level was established a priori at an alpha of 0.05. We employed an intention-to-treat analysis approach. We tested our secondary outcome of the standardized change score in 6MWT from baseline and 2 months also using linear mixed models, with the same approach. The covariate association of depression and self-efficacy for step count difference and 6MWT were also considered to be secondary questions of interest.

Since our analysis included a small amount of missing data for the covariates (education missing on 8%, all other covariates <4%), our analyses used multiple imputation by chained equations, using 5 imputations. Results differed very little compared to complete case analysis.

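### The stated times for app installation, eligibility and baseline do not fit together, so baseline in the MVN arm may follow allocation and app start, and day 1 of the 60-day step window is undefined.

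*Protocol*

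**What the plan says.** Four places bear on timing.

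- **Protocol, MVN Group Only:** "During the final week of outpatient cardiac rehabilitation, the MVN application will be downloaded" on to the participant's phone or tablet. This applies to the intervention arm alone.
- **Protocol, Inclusion criteria, item 3:** "Within eight weeks of completing outpatient cardiac rehabilitation". It does not say whether the eight weeks lie before completion, after it, or both.
- **Protocol, Both Usual Care and MVN Intervention groups:** the list opens "Upon completion of the CR program, participants will be given their standard instructions and educational handouts". It then gives the exit interview, "Baseline clinical measurements, including a 6 minute walk", and "An activity tracker will be given to each participant". The baseline and tracker items carry no date of their own.
- **Protocol, Study Activities table:** educational materials, questionnaires and the 6-minute walk are all placed at baseline. The app, the tracker and the prompts are placed in the intervention period, defined only as "Intervention period: 2 months".

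The SAP analyses the "step count difference between the two groups over 60 days" from daily counts, and the change in 6MWT from baseline to 2 months. It lists depression, self-efficacy and self-reported physical activity as candidate covariates. Neither document gives the date of randomisation, the order of randomisation, baseline, device hand-out and app activation, or the event that starts the 60 days.

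**The concern.** A baseline used in a change score, or as a covariate, should be measured before the participant knows the allocation and before any part of the intervention starts. Only MVN participants receive the download, so allocation must be known by the time it is done. If baseline then follows at CR completion, MVN participants take an effort-dependent walk test and complete self-report questionnaires knowing their arm, possibly with the app already in use. Nothing comparable happens in the control arm.

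Two analyses are exposed. The baseline walk enters the secondary 6MWT change score directly. The three baseline psychosocial and activity measures may enter the adjusted models, which assume that they precede treatment.

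The step outcome raises a related question. The protocol's own rationale is that activity often falls after discharge from CR, so supervised days and later days are not interchangeable. With no day 1, the reader cannot tell which kind of day the 60-day window contains.

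**Working it through.** The plan states no figure on this point to reproduce. The check sets the passages side by side and does date arithmetic on the stated windows.

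**Step 1: where baseline falls.** The shared list gives the educational handouts at CR completion. The Study Activities table places educational materials at baseline, the same label it gives the walk test and questionnaires. Together these put baseline at CR completion. This is an inference from two places, not a stated rule.

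**Step 2: try both readings of the eight-week criterion.**

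| Reading | Consequence for final-week installation |
|---|---|
| Enrolment after completion | Cannot be done: the final week has passed before the person enters. On the last eligible day, 8 × 7 = 56 days after completion, the installation window is 56 to 56 + 7 = 63 days in the past. |
| Enrolment before completion | Can be done, but the download precedes a completion-day baseline by up to 7 days. |

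Neither reading makes the three timings consistent with a baseline taken before treatment.

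**Step 3: size of the overlap.** The largest lead of download over baseline is 7 days. Against the 60-day step window that is 7/60 = 11.7%. This is a length of time, not a bias. It would be a share of the step window only if counting began at download, which the documents do not say.

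**Step 4: direction for the 6MWT.** Change = month-2 walk − baseline walk. If early app use raised the baseline walk, the MVN change would shrink, which works against the intervention. If knowing the allocation lowered effort at baseline, the MVN change would grow. The documents do not allow a choice between these.

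**Step 5: start of step counting.** Steps come from the tracker, not the app. Trackers are handed out to both arms in one item of the shared list, and the table gives both arms the same interval. A common start is therefore possible, but no text fixes it.

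**Step 6: could time since CR differ materially between arms?** Assume 30 per arm and entry uniform over 0 to 8 weeks after completion.
- SD of entry time = 8/√12 = 2.31 weeks.
- SE of the difference between arms = 2.31 × √(2/30) = 0.60 weeks.
- 95% range for chance imbalance = ±1.96 × 0.60 = about ±1.2 weeks.
- A gap of 4 weeks would be 4/0.596 = about 6.7 SE.

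Under these assumptions randomisation would not produce a large gap in time since CR. What remains is random error, not systematic bias.

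**The case against.** The strongest reply is that the final-week download is only set-up. The text dates the download and not first use. The table confines app and prompts to the intervention period, and the content is described as instructions for the time after CR. Download, then baseline, then use would fit all of that. The phrase about CR completion also opens only the first item of the shared list, which goes on to cover 2-month measurements and payments, so it cannot date every item.

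Much of this stands. Exposure to the app before baseline is possible, not stated, and the link between baseline and completion is inferred. But the reply does not deal with knowledge of allocation, which a download given to one arm reveals whether or not the app is in use. Nor does it make final-week installation workable for someone enrolled later.

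A reader might also infer that the MVN step window starts in the final week of CR while the control window starts at completion, so that the primary comparison is biased. The documents do not support this: no text gives MVN participants a Fitbit in the final week or starts control counting at completion, and the trackers share one hand-out item. Nor do they support a systematic gap between arms in time since CR, because one eligibility window and computer randomisation apply to both.

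Finally, the SAP is written in the past tense, so re-ordering procedures may no longer be possible for this trial. That changes the form of the remedy, not the need for it.

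**Conclusion.** The inconsistency is real and should be resolved. Followed literally, the protocol either cannot be carried out (enrolment after completion) or lets disclosure of allocation, and possibly app use, precede baseline by up to 7 days in the MVN arm only (enrolment before completion). The second case rests on baseline being taken at CR completion, which the protocol implies but does not state.

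The measures at risk are the 6MWT change score and the baseline depression, self-efficacy and self-reported activity covariates. Neither direction nor size can be computed from the documents.

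For the primary step outcome the finding is narrower: day 1 is undefined, so unequal starts or inclusion of supervised-CR days cannot be excluded. That the arms had different start days, or that the primary comparison is biased, is not shown.

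**What to change.** 1. Reconcile the three protocol passages on installation, eligibility and baseline. The choice of installation time is the sponsor's.
2. Whichever time is kept, complete all baseline tests before allocation is disclosed and before the app is activated. Where the trial has already run, report the actual order and the number of participants for whom this was not done, with a sensitivity analysis of the 6MWT result leaving them out.
3. In the SAP, define day 1 of the step window as the first full day after device hand-out, identically in both arms, and exclude from the 60 days any day still within supervised CR.
4. Optionally, for precision, include weeks from CR completion to randomisation as a pre-specified covariate, not a step-wise candidate.

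The cost is wording in both documents and, if item 4 is taken up, 1 degree of freedom. CR completion and enrolment dates are needed for eligibility anyway. Randomisation, hand-out and activation dates must also be available.

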**[name], MS, FNP-BC, FAAN, FAHA**

**NCT03446313**

**Statistical Analysis**

**04/23/2019**

P-values for baseline tests were calculated from two-sample t-tests (or Wilcox rank-sum test if skewed) or chi-squared tests.

We analyzed the primary outcome of step count difference between the two groups over 60 days fitting linear mixed-effects models with the step count for each day in R (version 3.6.0). For a more precise estimate of the treatment effect, we used a step-wise procedure to include potential covariates impacting the outcome (age, gender, working status, college or higher education, relationship status, depression, self-efficacy, and self-reported PA), including only terms that were significant in the model. The 2-sided significance level was established a priori at an alpha of 0.05. We employed an intention-to-treat analysis approach. We tested our secondary outcome of the standardized change score in 6MWT from baseline and 2 months also using linear mixed models, with the same approach. The covariate association of depression and self-efficacy for step count difference and 6MWT were also considered to be secondary questions of interest.

Since our analysis included a small amount of missing data for the covariates (education missing on 8%, all other covariates <4%), our analyses used multiple imputation by chained equations, using 5 imputations. Results differed very little compared to complete case analysis.

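### Covariates in the adjusted step-count model, and probably the 6MWT model, are kept only if significant, which modestly distorts the adjusted treatment effect in a way that depends on an unstated detail

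*SAP*

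**What the plan says.** The Statistical Analysis section of the SAP gives the purpose of adjustment as "For a more precise estimate of the treatment effect". The method follows: "we used a step-wise procedure to include potential covariates impacting the outcome", with eight named candidates (age, gender, working status, education, relationship status, depression, self-efficacy and self-reported physical activity), "including only terms that were significant in the model". The test level is fixed: "The 2-sided significance level was established a priori at an alpha of 0.05". The 6MWT change score is analysed "also using linear mixed models, with the same approach". The SAP adds: "The covariate association of depression and self-efficacy for step count difference and 6MWT were also considered to be secondary questions of interest". Missing covariate values are handled by imputation: "our analyses used multiple imputation by chained equations, using 5 imputations".

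The protocol (Selection of Subjects / Setting) caps enrolment at 60 in two randomised groups. Its Study Activities table schedules the psychosocial questionnaires at baseline and at month 2, and Aim 2 makes depression and self-efficacy outcomes of the trial.

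The SAP does not state:
- whether treatment was in the model during selection;
- the direction of selection or the numerical threshold;
- how one model was reached across the five imputed datasets;
- whether the unadjusted or the adjusted result is primary;
- when the depression, self-efficacy and activity covariates were measured.

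**The concern.** The outcome data that test treatment also decide which covariates enter the model. Naming the candidates in advance does not remove this, because the fitted subset still depends on the outcome. Two different errors can follow.

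- **Treatment in the model during selection.** Covariates survive when their sample association happens to be large. The fitted residual variance is then too low, and the standard error takes no account of the search. The estimate stays unbiased but the test is liberal.
- **Covariates chosen first, treatment added afterwards.** A covariate that is unbalanced between arms by chance can be selected because it carries part of the treatment effect. The test keeps its level but the estimate is pulled toward zero.

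Either could matter for a borderline result in a trial of this size, and the reader cannot tell which applies to the adjusted result. There is also a side issue. Depression and self-efficacy are both candidates that the rule may drop and secondary questions in their own right, and no separate model is stated for them.

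**Working it through.** **Plan's own figure.** The only figure to compare with is the two-sided 0.05. The documents give no power, SD or sample-size derivation to reproduce.

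**Inputs from the documents.** At most 60 participants, two groups, eight candidates, only significant terms kept, alpha 0.05.

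**Assumptions.** 30 per arm; four binary and four continuous candidates; backward elimination at p<0.05; one mean per participant; no serial structure in daily counts. The prognostic strengths (correlations with outcome) are assumed in four scenarios: all noise; two candidates at 0.4; all eight at 0.2; mixed (0.2, 0, 0.2, 0, 0.3, 0.4, 0, 0.2). Each was run 20,000 times, giving a Monte Carlo SE of sqrt(0.05 × 0.95 / 20,000) = 0.0015.

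| Independent candidates | Noise | Two at 0.4 | Eight at 0.2 | Mixed |
|---|---|---|---|---|
| Treatment in: type I error | 0.055 | 0.061 | 0.077 | 0.067 |
| Treatment in: model SE / true SD of estimate | 0.97 | 0.96 | 0.90 | 0.93 |
| Treatment out: type I error | 0.047 | 0.052 | 0.051 | 0.050 |
| Treatment out: shrinkage at 0.5 SD | 3.1% | 3.5% | 10.0% | 6.7% |
| Treatment out: shrinkage at 0.8 SD | 2.8% | 3.6% | 9.5% | 6.6% |
| Fixed eight: type I error | 0.047 | 0.052 | 0.051 | 0.049 |

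**Consistency check.** If the SE is too small by a ratio r, the type I error is about P(|t| > 2.00 × r) on roughly 55 degrees of freedom. For r = 0.90 the cut-off is 1.80 and the probability 0.077. For r = 0.93 it is 1.86 and 0.068. The understated SE therefore accounts for the excess.

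**Sensitivity.**
- With candidates correlated at 0.3 (noise, eight at 0.2, mixed), type I error with treatment in is 0.058, 0.066 and 0.066. Shrinkage at 0.8 SD with treatment out is 2.9, 5.9 and 6.7%.
- With unequal numbers of days (10 to 60 each, assumed ICC 0.5), type I error with treatment in is 0.055, 0.056, 0.077 and 0.068. Shrinkage at 0.8 SD with treatment out is 2.9, 3.7, 9.5 and 6.8%.
- With other assumed strengths (none; one covariate with R² 0.30; eight weak with total R² 0.30; 24,000 runs), backward elimination with treatment in gives 0.058, 0.058 and 0.075. Forward selection gives 0.053 to 0.075 (8,000 runs).

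**Power.** With treatment out and eight at 0.2, power at 0.5 SD is 50%, against 57% with the eight fixed.

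**Price of a fixed set.** The 95% CI half-widths, in SD units, are:

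| Scenario | Step-wise (treatment in) | Fixed eight | Unadjusted | Fixed / step-wise | Fixed / unadjusted |
|---|---|---|---|---|---|
| Noise | 0.508 | 0.556 | 0.514 | 1.09 | 1.08 |
| Two at 0.4 | 0.428 | 0.458 | 0.514 | 1.07 | 0.89 |
| Eight at 0.2 | 0.447 | 0.458 | 0.515 | 1.025 | 0.89 |
| Mixed | 0.423 | 0.441 | 0.515 | 1.04 | 0.86 |
| Noise, correlated | 0.507 | 0.556 | 0.514 | 1.10 | 1.08 |
| Eight at 0.2, correlated | 0.482 | 0.522 | 0.514 | 1.08 | 1.02 |
| Mixed, correlated | 0.448 | 0.471 | 0.515 | 1.05 | 0.915 |

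The noise row agrees with the closed form t50/t58 × sqrt(57/49) = (2.009/2.002) × 1.079 = 1.08. If only 50 are analysed it becomes t40/t48 × sqrt(47/39) = 1.10.

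**Associations, if read from the selected model.** A covariate with true correlation 0.2, 0.3 or 0.4 is retained in 33, 66 or 89% of trials. When retained, it is estimated at 1.69, 1.24 or 1.06 times its true value (6,000 runs each).

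**The case against.** The strongest reply is that the effect is small and may not touch the primary test. With no prognostic candidates or two strong ones, type I error is only 0.055 to 0.061. The 0.077 needs all eight candidates to be independent and weakly prognostic, and falls to 0.066 if they correlate at 0.3. This stands, and it is why the point is called modest.

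Several stronger readings are tempting but unsupported:

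- **The primary test is distorted one way or the other.** The SAP does not say this. The words "For a more precise estimate of the treatment effect" may imply an unadjusted base model first. If that model is primary, its test has neither problem.
- **The 6MWT test is certainly affected.** "also using linear mixed models, with the same approach" could mean only the mixed model and intention-to-treat. Including the step-wise rule is the natural reading, not the only one.
- **The depression and self-efficacy associations are exaggerated.** That follows only if they were read from the selected model, which the SAP does not say.
- **Selection across five imputations makes the result unstable.** When selection was simulated in each dataset, the treatment estimate ranged over a median 0.04 to 0.40 SE across the five, against 0.26 to 0.38 SE with the eight fixed. These overlap, so this is a reporting gap.

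The sentence "Results differed very little compared to complete case analysis" does not answer the point. It compares imputed with complete-case results, not the step-wise model with a fixed or unadjusted one.

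It is also fair to object that all eight covariates are not the only remedy. Any fixed baseline set, or an unadjusted primary analysis, would remove the selection problem. The argument for the eight is that they are the SAP's own list, so no new choice is made after the data are known.

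**Conclusion.** The concern holds for the adjusted treatment effect. The SAP states an outcome-driven selection rule, so this is more than a missing detail. At 60 participants it produces either a type I error of about 0.055 to 0.077 with an SE about 3 to 10% too small, or a type I error near 0.05 with a real effect understated by about 3 to 10%. Which one applies turns on whether treatment was in the model during selection. Whether the primary test is affected at all turns on which model is primary.

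The sizes rest on assumed prognostic strengths, 1:1 allocation, a p<0.05 threshold and no modelling of serial dependence in daily counts. The qualitative result does not depend on the exact strengths, since both branches appear in every scenario. The change is worth making because it is cheap and the trial is small, but nothing here shows that the trial's conclusion is wrong.

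**What to change.** **Change the model.** Replace the step-wise rule, for both step count and 6MWT, with a fixed set of baseline covariates kept in every imputed dataset whatever their significance. The SAP's own eight, at their baseline values, avoid any new choice. Month-2 depression, self-efficacy or self-reported activity must not be used, because they are measured after randomisation and the intervention may change them.

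**Report.**
- Give the unadjusted estimate beside the adjusted one, whatever either shows, and state which is primary.
- Label the step-wise model exploratory.
- State the direction and threshold of selection, whether treatment was in the model, and how one model was chosen across the five imputations.
- If the depression and self-efficacy associations came from the selected model, estimate them in a model that keeps those terms. The fixed-eight model does so.
- The SAP describes a completed analysis, so disclose the re-fit as post hoc. It cannot restore prespecification.

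**Cost.** Revised wording and one re-fit per model. The fixed-eight interval is about 2.5 to 10% wider than the step-wise one. Against the unadjusted interval it is about 8% wider if no candidate is prognostic (power at 0.5 SD falls from about 47% to 42%), about 2% wider for eight weak correlated candidates, and about 8.5 to 14% narrower in the other prognostic scenarios.

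### The 6MWT change-score analysis does not adjust for baseline 6MWT, so the arm contrast on this secondary outcome is usually somewhat less precise than the collected data allow

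*SAP*

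**What the plan says.** In the SAP's Statistical Analysis section, the reason for covariate adjustment is precision: "For a more precise estimate of the treatment effect, we used a step-wise procedure to include potential covariates impacting the outcome". The candidates are "age, gender, working status, college or higher education, relationship status, depression, self-efficacy, and self-reported PA", which makes eight, and the rule is "including only terms that were significant in the model". These sentences describe the step-count model. For 6MWT the SAP says: "We tested our secondary outcome of the standardized change score in 6MWT from baseline and 2 months also using linear mixed models". The same sentence carries the procedure over: "also using linear mixed models, with the same approach". No sentence adds baseline 6MWT as a covariate.

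The SAP has a further use for two of the candidates: "The covariate association of depression and self-efficacy for step count difference and 6MWT were also considered to be secondary questions of interest".

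The protocol collects what is needed. Under the heading for both the Usual Care and MVN groups it lists "Baseline clinical measurements, including a 6 minute walk" and repeats the clinical measurements at two months. The Study Activities table marks the 6 minute walk for both arms at Baseline and Month 2. Enrolment is capped at 60 (Selection of Subjects / Setting).

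**The concern.** A change score uses the baseline walk, but only by subtracting it in full, which fixes the baseline slope at 1. Month-2 distance usually regresses toward the mean on baseline distance, so the best slope is usually below 1. Full subtraction then adds back some baseline variation as noise. Putting baseline in the model lets the data choose the slope, at the cost of one degree of freedom.

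The SAP adjusts in order to gain precision, and the sample is small. It considers eight other covariates but not the baseline value of the outcome itself. What is at stake is the width of the confidence interval and the power for the 6MWT comparison, which is part of the protocol's first aim. Bias and type I error are not at stake: under randomization the arms have the same expected baseline, and the change-score contrast is unbiased.

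**Working it through.** **Inputs from the documents.** Enrolment of up to 60; two randomized arms; two-sided alpha 0.05; walks at baseline and Month 2 in both arms. The documents give no SD, correlation, effect size or power for 6MWT, so there is no stated figure to reproduce.

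**Assumptions.** Correlation between the two walks rho = 0.5, 0.7 or 0.9. Baseline SD = 1 and Month-2 SD = k, with k = 0.9, 1 or 1.1. N = 60 paired walks (the ceiling) or 40. Allocation 30 per arm where power is computed.

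**Formulas.**
- Change score: variance = 1 + k² − 2·rho·k.
- Baseline-adjusted: variance = k²(1 − rho²) × [1 + 1/(N − 4)]. The bracket is the price of estimating the slope: 1 + 1/56 = 1.0179 at N = 60, and 1 + 1/36 = 1.0278 at N = 40.
- With k = 1 the ratio is (1 + rho)/2 times the bracket. At rho = 0.5 and N = 60: 0.75 × 1.0179 = 0.763, and √0.763 = 0.874, so the SE is 12.6% smaller.

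| N | k | rho | Variance ratio (adjusted / change) | Change in SE |
|---|---|---|---|---|
| 60 | 1 | 0.5 / 0.7 / 0.9 | 0.763 / 0.865 / 0.967 | −12.6% / −7.0% / −1.7% |
| 60 | 1.1 | 0.5 / 0.7 / 0.9 | 0.832 / 0.937 / 1.017 | −8.8% / −3.2% / +0.9% |
| 60 | 0.9 | 0.5 / 0.7 / 0.9 | 0.679 / 0.764 / 0.824 | −17.6% / −12.6% / −9.2% |
| 40 | 1 | 0.5 / 0.7 / 0.9 | 0.771 / 0.874 / 0.976 | −12.2% / −6.5% / −1.2% |
| 40 | 1.1 | 0.9 | 1.027 | +1.4% |

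**Worst case.** Before the bracket, the change-score variance minus the adjusted variance is (1 − rho·k)², which is never negative and is zero when rho·k = 1. The expected SE loss from adjusting therefore cannot exceed √1.0179 = +0.9% at N = 60 or √1.0278 = +1.4% at N = 40. With k = 1 the break-even is rho = 2/1.0179 − 1 = 0.965 at N = 60 and 0.946 at N = 40.

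**Simulation check.** Over 20,000 trials at 30 per arm, the variance ratios were 0.760, 0.866 and 0.971 at k = 1. At k = 1.1 they were 0.936 (rho 0.7) and 1.017 (rho 0.9). These agree with the formula.

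**With another covariate already in the model.** In 6,000 simulated trials per rho (N = 60, k = 1), a further covariate correlated 0.5 with both walks was kept in both models. The SD of the arm estimate with baseline, relative to without, was 0.866, 0.901, 0.942, 0.975 and 0.991 at rho 0.6, 0.7, 0.8, 0.9 and 0.95.

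**Power.** At 30 per arm, k = 1 and 80% power, the detectable difference in baseline SDs falls from 0.736 to 0.643 (rho 0.5), 0.570 to 0.530 (rho 0.7) or 0.329 to 0.324 (rho 0.9). Equivalently, a change-score test with 80% power would have 89.4%, 85.4% or 81.3% with baseline in the model.

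**Effect on the depression and self-efficacy questions.** Suppose depression correlates −0.3 with both walks and k = 1 (an illustration only). Its association with change is 0. Conditional on baseline, its coefficient is (−0.3 + 0.3·rho)/(1 − 0.09) = −0.165, −0.099 or −0.033 at rho 0.5, 0.7 or 0.9. The two models answer different questions.

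**The case against.** The strongest case against rests on the SAP's brevity.

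- **Standardized is not defined.** Dividing by a constant changes nothing above. If each visit was divided by its own SD, the k = 1 rows apply whatever the raw SDs were. If the score was residualized on baseline, the point largely disappears, but the text does not say so.
- **The mixed model is not described.** With one change score per person, a participant random intercept cannot be separated from residual error, so two visits may have been modelled. A two-visit model with a common baseline mean would use baseline about as efficiently as ANCOVA. Without that constraint, and with complete pairs, it gives the same contrast as the change score. The SAP names a change score and states no constraint.
- **The eight covariates are listed for step count.** For 6MWT the SAP says only that the approach is the same. Reading this as the same list is natural but not certain.
- **The consequence is small.** The outcome is secondary, there is no bias, and every magnitude rests on assumed correlations and SDs. At k = 1.1 and rho = 0.9, adjustment is slightly worse.
- **The analysis is finished.** The SAP is in the past tense and already reports that "Results differed very little compared to complete case analysis". A new model is therefore post hoc.

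The ambiguities and the modest size stand as limits on the point, but they do not overturn it. The possible gain is much larger than the bounded loss, and no stated feature of the analysis recovers that gain.

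**Conclusion.** The point holds. As written, the 6MWT arm contrast comes from a change score with no baseline term, although the baseline walk was collected and the SAP adjusts for the sake of precision. With 60 pairs and equal SDs, the SE could be about 13%, 7% or 2% smaller at rho 0.5, 0.7 or 0.9. The saving is larger if Month-2 walks vary less than baseline walks, and smaller or nil if the Month-2-on-baseline slope is near 1. These sizes depend on assumed correlations, SD ratios and pair counts. The ceiling on the loss, 0.9% at 60 pairs and 1.4% at 40, does not depend on the correlation or SD ratio. This is an efficiency weakness in a secondary analysis that should be addressed; it does not threaten validity.

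**What to change.** For the 6MWT arm contrast only, fit one further model with baseline 6MWT forced in and kept outside stepwise selection. Either form will do:
- ANCOVA of Month-2 distance on arm and baseline. Using change as the outcome gives the same arm contrast.
- A two-visit model with a common baseline mean.

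Report it beside the existing result as a labelled additional or sensitivity analysis, not as a replacement. Give the arm difference, its 95% CI and the number of paired walks. State how the change score was standardized and whether the existing mixed model took one score or two visits per person; if it already had a common baseline mean, saying so settles the matter.

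Keep the depression and self-efficacy associations with 6MWT in a separate model, or state that conditioning on baseline changes their meaning.

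The cost is one model and a few sentences. No new data are needed.
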